15.4 Exclusion of Women, Minorities, and Children (Special Populations)

Adults of any gender or racial/ethnic group may participate.

15.5 Subject Confidentiality

Subject confidentiality is strictly held in trust by the investigators, study staff, and the IND sponsor(s) and their agents. The study protocol, documentation, data, and all other information generated will be held in strict confidence. No information concerning the study or the data will be released to any unauthorized third party without prior written approval of the IND sponsor.

Information from this study and from a subject's medical record may be reviewed and photocopied by the FDA and/or state and federal regulatory agencies such as the OHRP as applicable, and the IRB of the Forsyth Institute. Information from this study and from a subject's medical record may be used for research purposes and may be published; however, a subject's name will not be used in any publications. A subject's data and samples will be protected by using coded designations only. The list that matches a subject's name to the code number will be kept in a password-protected computer file and destroyed permanently after study completion. A subject will not be personally identified by any of the research materials in this study.

The study monitor or other authorized representatives of NIDCR may inspect all study documents and records required to be maintained by the investigator, including but not limited to medical records (office, clinic, or hospital) for the study subjects. The clinical study site will permit access to such records.

15.6 Future Use of Stored Specimens and Other Identifiable Data

No specimens will be retained for future use.

16 DATA HANDLING AND RECORD KEEPING

The investigators are responsible for ensuring the accuracy, completeness, legibility, and timeliness of the data reported. All source documents should be completed in a neat, legible manner to ensure accurate interpretation of data. The investigators will maintain adequate case histories of study subjects, including accurate case report forms and source documentation.

Details of the study data system will be described in a separate Data Management Plan.

16.1 Data Management Responsibilities

The investigative team at the Forsyth Institute will be responsible for data management including data entry, data security, and specimen tracking. Unanticipated problems and AEs must be reviewed by the investigator or designee.

16.2 Data Capture Methods

Data will be captured and stored electronically in a study-specific, password-protected database, with data quality checks built into the system.

Data including medical and dental history, demographics, AEs, concomitant medications, oral examination results, and vital signs will be entered into a data system designed for this study. Clinical measurements including MGI, PD, GM-CEJ, BOP, and PI will be entered chairside to an electronic data form, using special software installed on a study-designated laptop computer. For chairside data collection, a data recorder will work with the study examiner to enter data during the oral examination. Data from laboratory test results and special assays will be recorded by the laboratory and entered into the data system by study staff.

16.3 Types of Data

Data for this study will include demographic and medical/dental history data, vital signs, information on concomitant medications, safety observations (records of AEs), oral examination findings, clinical outcome measures (i.e., PD, CAL, PI, MGI, BOP, plaque and gingivitis severity scores), safety laboratory and other laboratory values (i.e., IL-1 β in GCF, BLXA4-ME levels in plasma, SPM profiles in plasma and serum), and microbial identification data.

16.4 Schedule and Content of Reports

The primary outcome measures are the safety parameters, which will be assessed by recording all AEs and SAEs, as reported by subjects or observed by oral examination,

measurement of vital signs, and review of safety laboratory results. The clinical investigator and the IND sponsor will review these data and work with the data coordinating center to provide regular reports to NIDCR (the study funder), the DSMB, and the IRB. The NIDCR medical monitor will track safety data in real time. If the trial is terminated prematurely for any reason, an abbreviated report will be prepared. To ensure confidentiality, coding will be used to identify subjects.

16.5 Study Records Retention

Study documents should be retained for a minimum of 2 years after the last approval of a marketing application in an ICH region and until there are no pending or contemplated marketing applications in an ICH region, or until at least 2 years have elapsed since the formal discontinuation of clinical development of the investigational product. These documents should be retained for a longer period, however, if required by local regulations. No records will be destroyed without the written consent of the IND sponsor. It is the responsibility of the IND sponsor to inform the investigator when these documents no longer need to be retained.

Study records will be maintained for at least 3 years from the date that the grant final financial report is submitted to the National Institutes of Health (NIH).

16.6 Protocol Deviations

A protocol deviation is any noncompliance with the clinical study protocol, Good Clinical Practice, or Manual of Procedures requirements. The noncompliance may be on the part of the subject, the investigator, or study staff. As a result of deviations, corrective actions are to be developed by the study staff and implemented promptly.

These practices are consistent with investigator and sponsor obligations in ICH E6:

- Compliance with Protocol, Sections 4.5.1, 4.5.2, 4.5.3, and 4.5.4
- Quality Assurance and Quality Control, Section 5.1.1
- Noncompliance, Sections 5.20.1 and 5.20.2

All deviations from the protocol must be addressed in study subject source documents and promptly reported to NIDCR and the local IRB, according to their requirements. A completed copy of the Protocol Deviation Form must be maintained in the regulatory file, as well as in the subject's source document file. The principal investigator and study staff are responsible for knowing and adhering to the IRB requirements.

17 PUBLICATION POLICY

Following completion of the study, the investigator is expected to publish the results of this research in a scientific journal. Any publications based on the results of the trial will conform to the NIH Grants Policy and the publication policy of the Forsyth Institute. This study will comply with the *NIH Public Access Policy*, which ensures that the public has access to the published results of NIH-funded research. It requires scientists to submit final peer-reviewed journal manuscripts that arise from NIH funds to the digital archive PubMed Central upon acceptance for publication.

The International Committee of Medical Journal Editors (ICMJE) member journals have adopted a clinical trials registration policy as a condition for publication. The ICMJE defines a clinical trial as any research project that prospectively assigns human subjects to intervention or concurrent comparison or control groups to study the cause-and-effect relationship between a medical intervention and a health outcome. Medical interventions include drugs, surgical procedures, devices, behavioral treatments, process-of-care changes, and the like. Health outcomes include any biomedical or health-related measures obtained in patients or participants, including pharmacokinetic measures and AEs. The ICMJE policy requires that all clinical trials be registered in a public trials registry such as *ClinicalTrials.gov*, which is sponsored by the National Library of Medicine. Other biomedical journals are considering adopting similar policies. For interventional clinical trials performed under NIDCR grants and cooperative agreements, it is the grantee's responsibility to register the trial in an acceptable registry, so the research results may be considered for publication in ICMJE member journals. The ICMJE does not review specific studies to determine whether registration is necessary; instead, the committee recommends that researchers who have questions about the need to register err on the side of registration or consult the editorial office of the journal in which they wish to publish.

United States Public Law 110-85 (Food and Drug Administration Amendments Act of 2007), Title VIII, Section 801 mandates that a "responsible party" (i.e., the sponsor or designated principal investigator) register and report results of certain "applicable clinical trials," described as:

- Trials of drugs and biologics: controlled clinical investigations, other than Phase I investigations, of a product subject to FDA regulation;
- Trials of devices: controlled trials with health outcomes of devices subject to FDA regulation, other than small feasibility studies, and pediatric postmarket surveillance required by FDA.

National Institutes of Health grantees must take specific steps to ensure compliance with NIH implementation of the Food and Drug Administration Amendments Act of 2007.

Appendix A: Schedule of Events

APPENDIX A:

SCHEDULE OF EVENTS

Procedures	Screen	Enrollment/ Baseline Visit 1	Visit 2	Visit 3	Visit 4	Visit 5	Visit 6	F/U
	Day -10 to -1	Day 0	Day 3 ± 1 day	Day 7 ± 1 day	Day 14 ± 1 day	Day 21 ± 1 day	Day 28 ± 1 day	Day 90 ± 14 days
Obtain informed consent	X	X						
Medical/dental history	X ^{a,b}	X ^a	X	X	X	X	X	
Record concomitant medications and dental procedures	X	X	X	X	X	X	X	
Urine pregnancy test	X	X						
Vital signs ^c	X	X	X	X	X	X	X	
Intraoral and extraoral examinations	X	X	X	X	X	X	X	
Assessment of plaque and calculus	X							
Solicit adverse events			X	X	X	X	X	X
Modified gingival index	X	X			X		X	
Gingival crevicular fluid sample for IL-1 β		X			X		X	
Probing depth; measure GM-CEJ to determine clinical attachment level		X			X		X	
Bleeding on probing		X			X		X	
Plaque index		X			X		X	
Plaque samples to analyze oral flora		X			X		X	
Blood for plasma BLXA4-ME level and SPM profiling in serum and plasma		X					X	
Blood for eligibility or safety laboratory tests ^d	X				X		X	
Urine for eligibility or safety laboratory tests ^d	X				X		X	

Procedures	Screen Day -10 to -1	Enrollment/ Baseline Visit 1 Day 0	Visit 2 Day 3 ± 1 day	Visit 3 Day 7 ± 1 day	Visit 4 Day 14 ± 1 day	Visit 5 Day 21 ± 1 day	Visit 6 Day 28 ± 1 day	F/U Day 90 ± 14 days
Assess compliance			X	X	X	X	X	
Provide oral rinse		X	X	X	X	X		
Hygiene instructions or referral for periodontal treatment								X

F/U = safety follow-up telephone call; GM-CEJ = distance from free gingival margin to cementoenamel junction; IL-1 β = interleukin-1 β ; SPM = specialized pro-resolution mediator

- a Includes history of alcohol and tobacco use.
- b Includes demographic information.
- c Pulse rate, respiratory rate, blood pressure, and oral body temperature are collected at all visits marked with "X". Weight is collected at the Screening Visit and Visit 6 (Day 28).
- d The on-site medical monitor will review the results of safety laboratory tests to determine whether a laboratory test should be redrawn.

IL-1 β	Interleukin-1 β
LXA ₄	Lipoxin A ₄
MedDRA	Medical Dictionary for Regulatory Activities
MGI	Modified gingival index
OMAS	Oral Mucositis Assessment Scale
PD	Pocket depth
PI	Plaque Index
PSI	Plaque Severity Index
PT	Preferred Term
SAE	Serious Adverse Event
SAP	Statistical Analysis Plan
SBP	Systolic Blood Pressure
SD	Standard Deviation
SE	Standard Error
SOC	System Organ Class
TEAE	Treatment-Emergent Adverse Event

1. PURPOSE OF THIS DOCUMENT

This statistical analysis plan (SAP) for protocol NIDCR Protocol 14-020-E is being developed before database lock and the statistical analyses of the data. The objective of this document is to (1) briefly summarize the purpose of the study and study design, (2) detail the planned statistical methodology, (3) define original and derived variables necessary to complete the analyses, and (4) delineate the most appropriate summary tables, listings, and graphical displays to be included in the study report.

This SAP will be presented to the Principal Investigator for approval. The statistical analyses and their corresponding tables, listings, and figures, as outlined in this document will be presented to the PI at the completion of the study analyses.

2. PROTOCOL SUMMARY

2.1 Study Objectives

The primary objective is to evaluate the safety of an investigational compound, BLXA4-ME, topically applied for 28 days as a daily oral rinse in adults with gingival inflammation. Safety will be assessed by the incidence of adverse events, including mucosal inflammation and irritancy, and findings from oral examinations and safety laboratory tests. Additionally, subjects will be monitored for development or progression of periodontitis and oral flora will be analyzed to detect an increase in opportunistic organisms.

The secondary objective is to assess preliminary efficacy of the oral rinse, by monitoring changes in the plaque index (PI), modified gingival index (MGI), bleeding on probing (BOP), and levels of interleukin-1 β (IL-1 β) in gingival crevicular fluid (GCF).

2.2 Overall Study Design and Plan

This study has a randomized parallel placebo-controlled double-blind study design with one treatment arm and two control arms (placebo oral rinse, and no rinse controls). Subjects in the treatment (N=50) and placebo rinse (N=50) arms will be double-blinded and receive oral rinse (BLXA4-ME or placebo rinse) to be applied once daily after morning teeth brushing. The no-rinse control arm (N=25) will be blinded from the investigators and apply no oral rinse. Subjects will perform their randomized treatment for 28 days. Safety parameters will be assessed before treatment and at Days 3, 7, 14, 21, and 28 after the initial treatment. Efficacy parameters will be assessed before treatment and Day 14 and Day 28 after the initial treatment. Total duration of subject participation will be 3 months (in clinic visits through 28 days, and a follow-up safety phone call at 2 months after last product use).

The Study Flow Chart and the Schedule of Events can be found in Appendices 13.1 and 13.2, respectively.

2.3 Study Population

Approximately 125 healthy adult male and female subjects with gingival inflammation, determined by mean full mouth MGI of at least 2.0 at screening and baseline, will participate in the study.

2.4 Blinding

This is a double-blind study. The PI, study coordinators, study examiners, data managers, and statisticians will be masked to the assigned treatment. Subjects receiving oral rinse will not know whether they are in the active or placebo rinse group. The no-rinse control will be blinded only from the PI, study coordinators, and study examiners since it is not possible to blind the subject from not having an oral rinse. The product code may be broken for an individual subject if he or she experiences a serious adverse event (SAE) and cannot be adequately treated without knowing the identity of the study product. The study blind will be broken after database lock.

2.5 Sample Size Determination

Sample size determination is based on the power to detect AEs (a primary safety outcome) with additional consideration given to detecting post-baseline study arm differences with respect to the MGI (a secondary efficacy outcome).

The probability of observing a specific AE for the study's sample size can be estimated. This probability depends on the sample size within a treatment group and on the true underlying probability of an individual experiencing the specific AE in that treatment group. Table 2.5.1 summarizes the probabilities of observing an AE given a sample size and true underlying event rate. For example, if the true probability of a subject experiencing a specific AE is 5%, the probability of observing 1 or more of that specific AE within a treatment group of 40 subjects is 87.1%.

The study's test oral rinse, placebo oral rinse, and no-rinse control arms are assigned treatment group sample sizes of 40, 40, and 20 subjects, respectively. For the test oral rinse and the placebo oral rinse arms, a sample size of 40 subjects per treatment group should have probabilities of 80.5%, 87.1%, 91.6%, and 96.4% of observing an AE having underlying incidence probabilities of 4%, 5%, 6%, and 8%, respectively. The no-rinse control arm is considered to be of lesser importance and, thus, to conserve the overall sample size, is assigned a sample size of 20 subjects, which should have probabilities of 55.8%, 64.2%, 71.0%, and 81.1% of observing an AE having underlying incidence probabilities of 4%, 5%, 6%, and 8%, respectively. Thus, the above sample sizes of 40, 40, and 20 subjects should give adequate power (> 80%) to detect AEs that occur at true underlying frequencies of 4% or greater in the test and placebo oral rinse study arms, and adequate power (> 80%) to detect AEs that occur at true underlying frequencies of 8% or greater in the no-rinse control arm. Conversely, if no AEs occur with a sample size of 20 and 40 subjects then the upper one-sided 95% CI of the underlying AE incidence rate would be 14% and 7.5%, respectively.

Table 2.5.1 Probability of Observing One or More Adverse Events within a Study Arm

"True" Underlying Probability of an Individual Experiencing an Adverse Event	Probability of Observing One or More Adverse Events within a Study Arm	
	No-Rinse Control Study Arm (n = 20)	Test and Placebo Oral Rinse Study Arms (n = 40)
0.01%	0.20%	0.40%
0.10%	2.0%	3.9%
0.25%	4.9%	9.5%
0.50%	9.5%	18.2%
1.00%	18.2%	33.1%
2.00%	33.2%	55.4%
3.00%	45.6%	70.4%
4.00%	55.8%	80.5%
5.00%	64.2%	87.1%
6.00%	71.0%	91.6%
8.00%	81.1%	96.4%
10.0%	87.8%	98.5%

Sample size (n) refers to the final sample size per treatment group of enrolled subjects who complete the study.

Power estimates for the secondary efficacy endpoint (MGI) are found in Table 2.5.2. In this power analysis, MGI refers to the MGI scores averaged over all tooth sites within each subject and visit. The power estimates in the table are based upon 50,000 simulations of mixed models analyses. The mixed models simulations include the MGI as the dependent variable, and fixed effects for treatment group (test oral rinse, placebo oral rinse, and no-rinse control), visit (Baseline, Day 14, and Day 28), and their treatment group-by-visit interaction. The model includes random effects for subject using a compound symmetry variance structure (i.e., exchangeable covariance). These power analyses assume an overall within-study group standard deviation of 0.3 MGI units at each visit and a difference in the mean change from baseline MGI at 28 days between the test oral rinse and the placebo rinse or between the test oral rinse and the no-rinse control of 0.2 MGI units. Correlation of MGI within subject among visits was assumed to be 0.3. The treatment group sample sizes of 40, 40, and 20 subjects for the test oral rinse, placebo oral rinse, and no-rinse control arms, respectively, are estimated to have powers of 71% and 54% to detect significant differences of 0.2 in the mean MGI scores between the test oral rinse and placebo oral rinse study arms, and between the test oral rinse and the no-rinse control study arms, respectively. Even though these sample sizes would be considered under-powered for testing efficacy in a Phase 3 clinical trial, for this Phase 1/2 protocol, with efficacy as a secondary objective, these study sample sizes can provide evidence (significant or not) of efficacy and provide efficacy estimates with their associated standard deviations needed for planning future Phase 2 or Phase 3 trials.

It is estimated that 50, 50, and 25 subjects will need to be enrolled to have final sample sizes of 40, 40, and 20 subjects for the test oral rinse, placebo oral rinse, and no-rinse control study arms, respectively, assuming a 20% subject attrition rate before completing the study.

Table 2.5.2. Mixed Models Power Analysis for MGI (Secondary Efficacy Outcome) Showing the Power for Several Sample Size Scenarios

Enrolled and Eligible Subjects			Subjects after 20% Drop-out			Power (%)	
Test (n)	Placebo (n)	Control (n)	Test (n)	Placebo (n)	Control (n)	Trt – Placebo ^a	Trt – Control ^b
50	50	25	40	40	20	70.9	53.8

Control = no-rinse control study arm; MGI = modified gingival index; placebo = placebo oral rinse study arm; test = test oral rinse study arm; trt = treatment (placebo or test oral rinse) study arm.

a Trt-Placebo: Power (probability) for finding a statistically significant difference (alpha = 0.05) in the change from baseline MGI at 28 days between the test oral rinse and the placebo oral rinse study arms.

b Trt-Control: Power (probability) for finding a statistically significant difference (alpha = 0.05) in the change from baseline MGI at 28 days between the test oral rinse and the no-rinse control study arms.

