Sample size (n) refers to the final sample size per treatment group of enrolled subjects who complete the study.

Power estimates for the secondary efficacy endpoint (MGI) are found in [Table 12-2](#). In this power analysis, MGI refers to the MGI scores averaged over all tooth sites within each subject and visit. The power estimates in the table are based upon 50,000 simulations of mixed models analyses. The mixed models simulations include the MGI as the dependent variable, and fixed effects for treatment group (test oral rinse, placebo oral rinse, and no-rinse control), visit (Baseline, 14 Days, and 28 Days), and their treatment group-by-visit interaction. The model includes random effects for subject using a compound symmetry variance structure (i.e., exchangeable covariance). These power analyses assume an overall within-study group standard deviation of 0.3 MGI units at each visit and a difference in the mean change from baseline MGI at 14 or 28 days between the test oral rinse and the placebo rinse or between the test oral rinse and the no-rinse control of 0.2 MGI units. Correlation of MGI within subject among visits

was assumed to be 0.3. The treatment group sample sizes of 40, 40, and 20 subjects for the test oral rinse, placebo oral rinse, and no-rinse control arms, respectively, are estimated to have powers of 71% and 54% to detect significant differences of 0.2 in the mean MGI scores between the test oral rinse and placebo oral rinse study arms, and between the test oral rinse and the no-rinse control study arms, respectively. Even though these sample sizes would be considered under-powered for testing efficacy in a Phase 3 clinical trial, for this Phase 1/2 protocol, with efficacy as a secondary objective, these study sample sizes can provide evidence (significant or not) of efficacy and provide efficacy estimates with their associated standard deviations needed for planning future Phase 2 or Phase 3 trials.

It is estimated that 50, 50, and 25 subjects will need to be enrolled to have final sample sizes of 40, 40, and 20 subjects for the test oral rinse, placebo oral rinse, and no-rinse control study arms, respectively, assuming a 20% subject attrition rate before completing the study.

Table 12-2 Mixed Models Power Analysis for MGI (Secondary Efficacy Outcome) Showing the Power for Several Sample Size Scenarios

Enrolled and Eligible Subjects			Subjects after 20% Drop-out			Power (%)	

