Test (n)	Placebo (n)	Control (n)	Test (n)	Placebo (n)	Control (n)	Trt – Placebo ^a	Trt – Control ^b
50	50	25	40	40	20	70.9	53.8

Control = no-rinse control study arm; MGI = modified gingival index; placebo = placebo oral rinse study arm; test = test oral rinse study arm; trt = treatment (placebo or test oral rinse) study arm.

a Trt-Placebo: Power (probability) for finding a statistically significant difference (alpha = 0.05) in the change from baseline MGI at 14 or 28 days between the test oral rinse and the placebo oral rinse study arms.

b Trt-Control: Power (probability) for finding a statistically significant difference (alpha = 0.05) in the change from baseline MGI at 14 or 28 days between the test oral rinse and the no-rinse control study arms.

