12.5.2 Secondary Efficacy Analysis

The study is not fully powered to find statistical differences among the study arms with respect to the secondary efficacy outcomes. As such, the main objectives of the secondary efficacy analyses are to: 1) obtain some evidence of efficacy (either a statistically significant effect or a nonsignificant trend); 2) obtain estimates of the size and variance of possible treatment effects that can then be used to plan later Phase 3 clinical trials; and 3) explore which of several outcomes may best be used to measure efficacy. As secondary analyses, no corrections will be made for multiple comparisons.

The secondary efficacy measures of PI, MGI, IL-1 β , and percentage of tooth sites with BOP will be analyzed using mixed models with a random effect for subject, and fixed

effects for baseline value, visit, study arm, and a study arm-by-visit interaction. Contrast statements within the mixed models analyses will compare study arms with respect to the efficacy measures. These statistical models allow comparisons to be made between study arms, between visits, and between treatment groups at each visit. These mixed models analyses assume the efficacy outcomes are approximately normal in distribution. If residual analysis shows the normality assumption to be unreasonable for any efficacy outcomes, then generalized linear mixed models with the appropriate links and distributional assumptions will be used to analyze these efficacy outcomes.

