9.3.2.1 Secondary Efficacy Endpoints

Secondary analyses will test for treatment arm differences in the change from baseline of the efficacy outcomes: MGI, percent of tooth sites with BOP, PI, GSI, PSI, and IL-1 β , at the study Day 14 and 28. These secondary endpoints will be analyzed using mixed models with change from baseline of the whole mouth average of the efficacy endpoint as the dependent variable, subject as a random effect, a covariate adjustment for baseline, and fixed effects for visit, study arm, and a study arm-by-visit interaction.

The following SAS code using mixed models will be used to analyze the secondary endpoints: MGI, PI, GSI, PSI, IL-1 β (4-sample mean), and percent of sites with BOP.

```
Proc Mixed data=dataset;  
  class subject visit study_arm;  
  model change = baseline study_arm visit study_arm *visit ;  
  repeated visitn / sub=subject type=cs;  
  lsmeans study_arm*visit / pdiff;  
run;
```

where: change = change in the efficacy endpoints from baseline.

These mixed models analyses assume the efficacy outcomes are approximately normal in distribution. A compound symmetry variance structure is assumed for the mixed models; however, if the Schwarz Bayesian criterion indicates that an unstructured variance structure better fits the model then the unstructured variance structure for the repeated effects will be used. Residual analysis will test the underlying assumptions of the mixed models analyses. The choice of using the arithmetic 4-sample IL-1 β means or the geometric 4-sample IL-1 β means will be based upon the models with the better residual fit to model assumptions. If for any efficacy endpoint, the normality assumption is found to be unreasonable, then log-transformation will be used to normalize the data. Furthermore, if log-transformation fails to normalize the data then generalized linear mixed models with the appropriate links and distributional assumptions or will be used to analyze these efficacy outcomes.

Within the each of the mixed models analysis of the efficacy endpoints, pairwise contrasts will be made to test for statistical differences among the 3 study arms with respect to the change from baseline at the Day 14 and Day 28 visits. Further pairwise contrasts will test each endpoint for statistical differences between the Day 14 and Day 28 visits within each study arm.

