Since this is a safety phase 1 / 2 with safety measures as the primary endpoints, the secondary efficacy endpoints will not be adjusted for multiplicity. However, the contrast between the treatment and placebo rinse arms with respect to the MGI change from baseline at Day 28 will be considered the secondary endpoint of chief importance. The same statistical contrast but with BOP change from baseline as the dependent variable will be considered the statistical contrast next in order of importance.

Tables will summarize the p-values, contrasts, and least squares means (with standard errors) of the change from baseline and their differences among the treatment groups and visits for each of the mixed models analyses described above.

Summary statistics of the secondary endpoints and their change from baseline, including n, means, minimums, maximums, standard deviations, and standard errors, will be summarized in a table by study arm and study visit. Raw values of all the secondary efficacy endpoints, both on the tooth-site level and the subject level will be listed.

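### The stated MGI power (70.9% and 53.8%) belongs to a model without a baseline covariate; at the plan's own inputs the planned baseline-adjusted test has about 87% and 72%

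*SAP*

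**What the plan says.** **Power model.** Protocol section 12.3 and SAP section 2.5 describe the same simulation. In the SAP's words, "The mixed models simulations include the MGI as the dependent variable, and fixed effects for treatment group", visit (Baseline, Day 14, Day 28) and their interaction, with a compound symmetry structure. Baseline is a level of the visit factor and there is no baseline covariate. The stated result is that the groups "are estimated to have powers of 71% and 54% to detect significant differences of 0.2 in the mean MGI scores"; protocol Table 12-2 and SAP Table 2.5.2 give 70.9% and 53.8%.

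**Analysis model.** SAP section 9.3.2.1 takes change from baseline as the response, with "subject as a random effect, a covariate adjustment for baseline, and fixed effects for visit, study arm, and a study arm-by-visit interaction". Its PROC MIXED code has baseline in the model statement. Protocol section 12.5.2 likewise lists fixed "effects for baseline value, visit, study arm, and a study arm-by-visit interaction". The SAP then singles out "the contrast between the treatment and placebo rinse arms with respect to the MGI change from baseline at Day 28" as the secondary endpoint of chief importance.

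**Powered visit.** The protocol assumes "a difference in the mean change from baseline MGI at 14 or 28 days between the test oral rinse and the placebo rinse", and footnote a of Table 12-2 defines the power as that for a significant difference "in the change from baseline MGI at 14 or 28 days between the test oral rinse and the placebo oral rinse study arms". The matching SAP footnote reads "in the change from baseline MGI at 28 days between the test oral rinse and the placebo oral rinse study arms". The power figures are identical in the two documents.

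**The concern.** A power figure should describe the test that will be run. These are the only efficacy power figures in either document, and they come from a different model from the one planned for the chief efficacy contrast. With a within-subject correlation of only 0.3, an unadjusted change score is noisy. Adjusting for baseline removes much of that noise, so the two models differ materially in power.

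The consequence is one of interpretation. Both documents call these sample sizes under-powered by Phase 3 standards, and both want the efficacy results to inform the planning of later trials. A null MGI result reads differently when the test had 87% power than when it had 71%. The visit wording adds a second ambiguity: significance at either of two visits is a different event, with different power, from significance at Day 28.

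**Working it through.** **Inputs** (protocol section 12.3, SAP section 2.5): SD 0.3 at each visit; correlation 0.3 between visits; difference in mean change 0.2; completers 40/40/20; alpha 0.05. Sidedness is not stated. Two-sided reproduces the figures; one-sided gives 80.9%/66.0% and does not.

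**Step 1: reproduce the stated figures (no baseline covariate).**
- Variance of a change = 2 × SD² × (1 − ρ) = 2 × 0.09 × 0.7 = 0.126.
- Test vs placebo: SE = √(0.126 × (1/40 + 1/40)) = 0.0794, and 0.2/SE = 2.52.
- Test vs no-rinse: SE = √(0.126 × (1/40 + 1/20)) = 0.0972, and 0.2/SE = 2.06.
- Noncentral t with 194 df: 70.8% and 53.5%. A 20,000-trial simulation of the three-visit compound symmetry model gives 70.9% and 53.6%.

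These match the stated 70.9% and 53.8%. Using the enrolled numbers (80.4%/63.3%) or the post-treatment score alone (84.6%/68.2%) does not.

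**Step 2: the planned model (baseline covariate).**
- Residual variance given baseline = SD² × (1 − ρ²) = 0.09 × 0.91 = 0.0819.
- Test vs placebo: SE = √(0.0819 × 0.05) = 0.0640, and 0.2/SE = 3.13.
- Test vs no-rinse: SE = √(0.0819 × 0.075) = 0.0784, and 0.2/SE = 2.55.
- Noncentral t with 96 df: 87.2% and 71.4%.
- 20,000-trial simulations of the SAP model under compound symmetry: 87.1% to 87.6% and 71.6% to 72.0%. With an unstructured covariance, the SAP's fallback: 86.6% and 71.1%.

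| | Stated | Simulated model, reproduced (t) | Planned model (t) | Difference detectable at 80% power, simulated vs planned |
|---|---|---|---|---|
| Test vs placebo | 70.9% | 70.8% | 87.2% | 0.223 vs 0.181 |
| Test vs no-rinse | 53.8% | 53.5% | 71.4% | 0.274 vs 0.222 |

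**Step 3: dependence on the assumptions.** The values below, other than SD 0.3 and correlation 0.3, are assumptions made for this check.

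Planned-model power at correlation 0.3:

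| SD | Test vs placebo | Test vs no-rinse |
|---|---|---|
| 0.30 | 87.2% | 71.4% |
| 0.33 | 80.3% | 63.2% |
| 0.35 | 75.6% | 58.1% |
| 0.37 | 70.8% | 53.5% |
| 0.40 | 64.1% | 47.4% |

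Test vs placebo at SD 0.3:

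| Correlation | Unadjusted | Adjusted |
|---|---|---|
| 0.1 | 59.9% | 84.3% |
| 0.3 | 70.8% | 87.2% |
| 0.5 | 84.3% | 92.6% |
| 0.7 | 96.9% | 98.5% |

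**Step 4: the visit wording.** If the protocol meant significance at either visit, the unadjusted power by simulation would be 85.0%/70.0% with a 0.2 difference at both visits, or 72.4%/55.7% with the difference at Day 28 only. The stated figures fit a single-visit contrast.

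**The case against.** The strongest reply is that nothing was miscalculated. The simulation model is described in full, its result is correct, and neither document claims that it is the analysis model. A simpler power model that errs on the cautious side is common practice. Sample size rests on adverse event detection, efficacy is secondary and aimed at estimation, and a revised planning figure changes no test or estimate. All of that stands, and it limits how much the point matters.

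Two further objections concern the remedy. First, SAP section 9.3.2.2 expects that admitting subjects with periodontitis may increase variability, and a rise in SD from 0.30 to 0.37 cancels the whole gain, so a bare 87% would be less prudent than the current text. This also stands; any new figure needs a range of SDs beside it. Second, the under-powered remark is about Phase 3 standards in general, and test versus no-rinse stays near 71% to 72% even with adjustment. That supports leaving the remark in place for the secondary outcomes as a whole.

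On the visits, the protocol can be read as meaning either visit taken singly. With equal SD and correlation, power is then the same at Day 14 and Day 28. The reading is plausible and fits the number, but the text does not say so, and the SAP's section on changes from the protocol does not mention the rewording.

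None of this makes the stated power the power of the planned test.

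**Conclusion.** The point holds. The 70.9% and 53.8% are correct for the unadjusted three-visit model but understate the power of the baseline-adjusted analysis that both documents plan, by about 16 points for test versus placebo and about 18 for test versus no-rinse. This rests on the plan's SD of 0.3, correlation of 0.3, difference of 0.2, 40/40/20 completers and a two-sided 0.05 test. The size of the gap depends on the correlation: for test versus placebo it is about 24 points at 0.1, 8 at 0.5 and 2 at 0.7. The direction is conservative and no enrolment decision turns on it. It is worth correcting because the documents give no power figure for the planned test of their chief efficacy contrast, and because protocol and SAP attach the same figures to differently worded contrasts.

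**What to change.** - Rerun the simulation with the planned model (change from baseline, baseline covariate, arm, visit, arm-by-visit) for the single Day 28 contrast. Restate protocol Table 12-2 and SAP Table 2.5.2; expect about 87% and 72% at the current inputs.
- Show the result over a range of SDs, for example 0.30 to 0.40, and state that it depends on the assumed SD and correlation.
- If a rerun is not wanted, keep the existing figures and label them in both tables as unadjusted for baseline and conservative under the stated inputs.
- Change the protocol's text and table footnotes to Day 28, to agree with the SAP.
- Keep the protocol's statement that the study is not fully powered for the secondary outcomes as a whole. Qualify the under-powered remark only for MGI, test versus placebo.
- Minor, in the same SAP section: the upper bound after zero events is given as 14% for 20 subjects, which is the exact value (1 − 0.05^(1/20) = 13.9%), but as 7.5% for 40, which is 3/40. The exact value is 1 − 0.05^(1/40) = 7.2%. Use one method for both.

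The cost is one simulation rerun and edits to two tables with their footnotes and two paragraphs. Enrolment does not change.
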